Lumbar puncture is not done in all patients, due to contraindications, refusal of some patients to consent to an invasive and burdensome procedure, or guidelines not recommending CSF biomarkers in specific cases (e.g. no objective cognitive impairment and no other dementia risk indicators). State-of-the-art CSF biomarkers are estimated to be available via routine assessments in about 100-150 of the total 300 patients in the prospective study. Plasma biomarkers using benchmarking equipment (section 4.1.4 Benchmarking equipment for AD plasma biomarkers) will thus be measured in all 300 patients. For the retrospective study, existing plasma samples will be selected if CSF biomarker data is also available from routine assessments. Aspects related to

CSF biomarker assays used at each study centre are detailed below in section 4.1.4.1 State-of-the-art CSF biomarkers.

Blood

- Blood sampling procedures, i.e. routine sampling from all patients versus selected groups, sample storage for research purposes
- Current availability of AD blood biomarkers for routine clinical use
- Availability of kidney and liver function measurements, including list of relevant biomarkers

AD blood biomarkers are not currently available for routine clinical use at the study centres, except for plasma NFL in Finland provided by the UEF biomarker laboratory. Blood sampling is common at all study centres, especially as part of research studies. Kidney and liver function measurements are available either measured at the study centre or at primary care; creatinine and ASAT are common across all study centres.

A set of conditions for storage of existing samples applicable across study centres was identified (Table 4).

Neuroimaging

- Structural MRI procedures, i.e. routine for all patients versus selected groups
- Possibility to retrieve MRI-related data for research
- Availability and type of PET scans, and procedures (routine for all patients versus selected groups)

Structural brain MRI is done at all study centres, except in patients with MRI contraindications. Quantitative image analysis is not done as part of routine procedures but validated semi-quantitative visual rating scales (e.g. for hippocampus atrophy and white matter lesions) are used at all centres. PET scans (e.g. FDG-PET, amyloid-PET) are only done in selected cases due to higher cost.

B) Other assessments done as part of research

- Cognitive tests
- Daily life functioning level
- Other

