4.3.3. Recruitment

All clinical study centres have well-established recruitment procedures for research studies, including both HCPs and patients. Recruitment timeline for the 2D-BioPAD clinical pilot study is shown in section 4.5. Continuous recruitment will be conducted until a total sample of ≈ 300 patients will be reached. Step 1 (feasibility test-run) will include the first 30 recruited patients (10 per study centre). In Step 2, recruitment will be scaled up to include 270 patients until the total $N \approx 300$ is reached.

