4.3.5.3. Missing data

Missing data in the 2D-BioPAD prospective study is defined as:

- Missing blood samples and/or related AD biomarkers measured using the 2D-BioPAD diagnostic aid and/or benchmarking equipment. The three study centres have extensive experience with blood sampling for clinical research studies, which reduces the risk of sampling failures. A sufficient amount of blood will be collected to allow completion of AD blood biomarker measurements in case of technical issues with some of the samples.
- Missing answers from patients in self-reported questionnaires. Completion will be ensured by HCPs checking the questionnaires during the 2D-BioPAD baseline visit.
- Missing answers from HCPs in questionnaires. Technical solutions will be applied in the 2D-BioPAD digital interface to design the questionnaires in a way that reduces the potential to skip or miss questions.

Most data collected from patients in the 2D-BioPAD clinical pilot study will be data generated during the standard assessment procedures at each study centre. Since these data reflect real-world clinical routines, missing assessments will not be treated as missing data. A pre-defined core set of assessments will be conducted in the same way across all centres (section 4.3.4).

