4.4.2. Prospective study outcomes

Table 9. Overview of the prospective study outcomes

Outcome type	Description
Primary	
 Sensitivity, specificity, positive and negative predictive values of plasma biomarkers measured with the 2D-BioPAD prototype versus benchmarking equipment (same as above) for identifying AD diagnosis established as per centre-specific standard procedures. Overall experience of HCPs with the 2D-BioPAD diagnostic aid Overall experience of patients with the 2D-BioPAD diagnostic aid
Secondary	
 Comparison of plasma biomarker values between 2D-BioPAD prototype and benchmarking equipment, considering the potential impact of other parameters, e.g., demographics, comorbidities, disease stage Sensitivity, specificity, positive and negative predictive values of plasma biomarkers measured with the 2D-BioPAD prototype for identifying AD-related pathology (e.g., β-amyloid, tau), as indicated by either plasma biomarkers from benchmarking equipment or, where available, CSF biomarkers measured during routine assessments at the clinical study centres using state-of-the-art equipment. Investigating plasma biomarkers measured with 2D-BioPAD prototype versus benchmarking equipment in relation to cognitive, clinical and other data Assess if user experience (HCPs and patients) with the 2D-BioPAD diagnostic aid varies by country, clinical specialty, and/or years of experience Assess if the information provided to HCPs via the digital interface of the 2D-BioPAD diagnostic aid is understandable and relevant Collect feedback for diagnostic aid improvement from HCPs and patients

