4.4.3. Data analysis

Analyses will include e.g.:

- Correlations (Spearman/Pearson as appropriate) between 2D-BioPAD markers and benchmarking plasma markers. Statistical tests for comparing correlation coefficients will be used where applicable.
- Linear regressions and plots of 2D-BioPAD markers and benchmarking plasma markers.
- Bland-Altman comparison of 2D-BioPAD markers against benchmarking plasma markers.

Between-group comparisons of 2D-BioPAD AD plasma biomarker levels will be conducted using e.g., Mann-Whitney U test, t-test, or ANOVA as appropriate. Groups will be defined according to both clinical and biomarker-based characteristics. Diagnostic groups will be based on diagnosis established following centre-specific standard assessments, e.g., AD dementia, other dementia, MCI, or control. Biomarker-based groups will be defined using:

- For all participants, AD blood biomarkers measured with benchmarking equipment. Cut-offs will be based on existing literature (where available) and/or data-driven, e.g., using Gaussian mixture modelling.
- For participants with available AD CSF biomarkers from standard assessments, grouping will be based on established cut-offs.
- Exploratory analyses will consider ATN-based categorizations using state-of-the-art CSF and/or benchmarking plasma biomarkers.

To assess the potential impact of other parameters, e.g., demographics, comorbidities, liver and/or kidney function, APOE genotype (where available), such parameters will be added as covariates in the analyses.

Discrimination accuracies of 2D-BioPAD AD plasma biomarkers will be determined with logistic regression models and receiver operating characteristic curve (ROC) analysis. When predicting diagnosis or CSF-based biomarker +/- status, for each AD blood biomarker the area under the receiver operating characteristic curve (AUC) of the ROCs for 2D-BioPAD and benchmarking measures will be compared with DeLong test. Sensitivity, specificity, positive and negative predictive values will be assessed for different 2D-BioPAD biomarker cut-offs. Initial analyses will consider each AD plasma biomarker individually. Further analysis will investigate combinations of plasma biomarkers to determine which combinations have the best discrimination accuracy.

AD plasma biomarkers (2D-BioPAD versus benchmarking equipment) will be investigated in relation to cognitive, clinical, and other data using appropriate regression models.

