Unadjusted 2-sided p-values <0.05 will be considered statistically significant. Adjustment for multiple testing using a false discovery rate (e.g., Benjamini-Hochberg procedure) will be used where relevant.

The main hypothesis is that the accuracy of the 2D-BioPAD system measurements is noninferior to the accuracy of AD plasma biomarkers measured using benchmarking equipment.

Analyses of user experience (HCPs and patients) will include mainly descriptives, with comparisons by country, clinical specialty, and/or years of experience where relevant.

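### One secondary outcome counts agreement with the benchmark plasma assay as accuracy for AD pathology, and its CSF alternative covers only a clinically selected third to half of patients

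*Protocol*

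**What the plan says.** Protocol section 4.4.2, Table 9, has a secondary outcome giving sensitivity, specificity, PPV and NPV of 2D-BioPAD for AD-related pathology, "as indicated by either plasma biomarkers from benchmarking equipment or, where available, CSF biomarkers measured during routine assessments". Neither reference is ranked above the other.

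Section 4.4.3 forms biomarker-based groups in two ways. The first is "For all participants, AD blood biomarkers measured with benchmarking equipment", with cut-offs taken from the literature and/or derived from the data. The second, for patients who have CSF, uses established cut-offs. The main hypothesis in the same section is that 2D-BioPAD accuracy is "noninferior to the accuracy of AD plasma biomarkers measured using benchmarking equipment".

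On CSF, section 4.1.3 says: "State-of-the-art CSF biomarkers are estimated to be available via routine assessments in about 100-150 of the total 300 patients". Lumbar puncture is not done where there is a contraindication, where the patient refuses, or because of "guidelines not recommending CSF biomarkers in specific cases (e.g. no objective cognitive impairment and no other dementia risk indicators". Section 4.3.5.3 adds, for routine data: "Since these data reflect real-world clinical routines, missing assessments will not be treated as missing data".

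The outcome of the same kind in the retrospective stage (Table 8, section 4.4.1) uses CSF with established cut-offs as its only pathology reference.

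**The concern.** Two different quantities sit under one label. Scored against CSF, 2D-BioPAD gets an estimate of accuracy for pathology. Scored against benchmark plasma, it gets a measure of how often two blood assays for the same analytes agree. Errors that both assays make in the same patient count as correct results. Errors made only by the benchmark count against the device. The result can lie on either side of the true accuracy, and nothing in the study data alone shows which side.

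The CSF part has a separate limit. The cohort includes patients with subjective complaints only, and section 4.1.3 names absence of objective impairment as a reason not to puncture. The subset with CSF will therefore probably be more impaired than the cohort. Predictive values depend directly on prevalence, so they would not carry over to the referred population. The rule in section 4.3.5.3 takes absent routine assessments out of missing-data handling, and for this outcome the absent assessment is the reference standard.

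Sections 2 and 5 say that the results will be used to plan confirmatory studies, so a mislabelled accuracy figure would be carried forward.

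**Working it through.** **What can be reproduced.** The protocol gives no accuracy, prevalence or power inputs, so its sample size cannot be re-derived. The counts are consistent: 3 × 100 = 300 and 30 + 270 = 300. The expected CSF share is 100/300 = 33% to 150/300 = 50%, which leaves 150 to 200 patients without CSF. All accuracy, prevalence and puncture rates below are assumptions.

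**Step 1: benchmark plasma as the reference.** Assume true sensitivity/specificity of 0.80/0.80 for the device and 0.85/0.85 for the benchmark, and pathology prevalence 0.45. Let φ be the correlation between the two results within patients of the same pathology status, and c = φ × √(0.85 × 0.15 × 0.80 × 0.20) = φ × 0.1428.

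- Benchmark positive: 0.45 × 0.85 + 0.55 × 0.15 = 0.465
- Both positive: 0.45 × (0.85 × 0.80 + c) + 0.55 × (0.15 × 0.20 + c) = 0.3225 + c
- Apparent sensitivity = (0.3225 + c) / 0.465
- Benchmark negative: 1 − 0.465 = 0.535
- Both negative: 0.45 × (0.15 × 0.20 + c) + 0.55 × (0.85 × 0.80 + c) = 0.3875 + c
- Apparent specificity = (0.3875 + c) / 0.535

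| φ | c | Apparent sensitivity | Apparent specificity |
|---|---|---|---|
| 0 | 0 | 0.69 | 0.72 |
| 0.5 | 0.0714 | 0.85 | 0.86 |
| 0.7 | 0.1000 | 0.91 | 0.91 |

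The true value is 0.80 in every row. A second set of assumptions (device 0.90/0.90, benchmark 0.80 to 0.95, prevalence 30% to 60%, errors from independent to maximally shared) gives apparent sensitivity from 0.61 to 1.00 and specificity from 0.68 to 1.00.

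**Step 2: the CSF subset.** Assume 100 patients each with subjective complaints, MCI and dementia, with pathology prevalence 0.2, 0.5 and 0.7. The cohort then has 20 + 50 + 70 = 140 patients with pathology and 160 without.

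*Device accuracy constant at 0.90/0.90.*
- Full cohort: PPV = 126/(126 + 16) = 0.887; NPV = 144/(144 + 14) = 0.911.
- CSF in 5%, 45% and 50% of the three groups (100 patients): 1 + 22.5 + 35 = 58.5 with pathology and 41.5 without. PPV = 52.65/(52.65 + 4.15) = 0.927; NPV = 37.35/(37.35 + 5.85) = 0.865.
- Over four such puncture patterns giving 100 to 150 CSF results, PPV is 0.921-0.927 and NPV 0.865-0.875. Sensitivity and specificity stay at 0.90/0.90.

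*Accuracy varying by stage (sensitivity 0.80/0.90/0.95, specificity 0.95/0.90/0.80).*
- Full cohort: sensitivity = (16 + 45 + 66.5)/140 = 0.911; specificity = (76 + 45 + 24)/160 = 0.906.
- Same 100-patient subset: sensitivity = (0.8 + 20.25 + 33.25)/58.5 = 0.928; specificity = (3.8 + 20.25 + 12)/41.5 = 0.869.
- Over the same patterns, sensitivity is 0.922-0.928 and specificity 0.869-0.878.

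**Step 3: precision if CSF is the only pathology reference.** At an assumed sensitivity of 0.90 and prevalence of 40% to 60%, the Wilson 95% half-width is 0.077-0.095 with 100 CSF results, 0.063-0.077 with 150, and 0.044-0.054 if all 300 had CSF.

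**Step 4: a trap in the remedy.** Suppose CSF status were imputed from stage and benchmark result but not from the device result. Take two equally accurate tests (0.85/0.85) with independent errors, the stage prevalences of Step 2, and puncture rates of 10%, 55% and 60% (125 of 300). The device then comes out at 0.75/0.77. With the device result added to the imputation model, it returns to 0.85/0.85.

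**The case against.** The strongest reply is that the reach is small. The DeLong comparison of device and benchmark AUCs in section 4.4.3 is confined to predicting diagnosis or CSF status. The prospective primary accuracy outcome uses clinical diagnosis. The retrospective stage uses CSF only, and every retrospective sample is chosen to have it. All of this stands. A reader might infer that the benchmark is scored against itself, or that the non-inferiority hypothesis is decided against its own comparator; the document plans neither.

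A reader might also infer classical verification bias, with the device result influencing who gets a lumbar puncture. Section 4.3.2 excludes that route: the 2D-BioPAD visit follows completion of the standard assessments and the diagnosis. Selection works through clinical features, so sensitivity and specificity move only if device accuracy varies with those features. That variation is plausible but not established, and in the example above it moves them by about 1 to 2 and 3 to 4 points.

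Nor does the protocol say that the two references will be pooled, or that the CSF-subset result will be presented as accuracy in the whole cohort. Section 4.1.3 discloses the subset and the reasons for selection. Details of weighting or imputation may properly sit in an SAP that is not shown.

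What the reply does not reach is the outcome definition. Table 9 itself puts sensitivity, specificity, PPV and NPV for pathology on an assay-to-assay comparison, and Table 8 does not.

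**Conclusion.** The point holds for one secondary prospective outcome. Its benchmark-referenced part is agreement under the name of accuracy, and may over- or understate true accuracy: 0.69 to 0.91 for a true sensitivity of 0.80, under the inputs assumed in Step 1. Comparisons of 2D-BioPAD levels between benchmark-defined groups (section 4.4.3) should likewise be read as agreement.

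Its CSF-referenced part describes a selected 33% to 50% of patients. If pathology is more common in that subset, PPV there is higher and NPV lower than in the referred population, by about 3 to 5 points in the example. A shift in sensitivity and specificity is conditional on accuracy varying with stage, so the outcome should not be called verification-biased without that condition.

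The directions and the distinction between agreement and accuracy follow from the design; the sizes rest on assumed accuracy, prevalence and puncture rates. For a secondary outcome in a pilot this is a change that should be made, not a threat to the main comparison.

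**What to change.** - In Table 9 and section 4.4.3, make CSF with established cut-offs the pathology reference for sensitivity, specificity, PPV and NPV, as Table 8 already does.
- Report 2D-BioPAD against benchmark-defined status separately, as positive and negative percent agreement.
- Present CSF-based accuracy as applying to patients selected for lumbar puncture.
- In section 4.3.5.3, exempt this outcome from the rule that absent routine assessments are not missing data.
- Add a sensitivity analysis weighting for the probability of having CSF, using data held on all patients (diagnosis, MMSE, age, centre). If imputation is used instead, its model must include both the 2D-BioPAD and the benchmark results; Step 4 shows why.

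No new procedures or patients are needed. The cost is protocol wording, modest extra analysis and somewhat wider intervals. Step 3 gives the unweighted widths for 100 to 150 CSF results, and weighting will widen them a little more.

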4.4.3. Data analysis

Analyses will include e.g.:

- Correlations (Spearman/Pearson as appropriate) between 2D-BioPAD markers and benchmarking plasma markers. Statistical tests for comparing correlation coefficients will be used where applicable.
- Linear regressions and plots of 2D-BioPAD markers and benchmarking plasma markers.
- Bland-Altman comparison of 2D-BioPAD markers against benchmarking plasma markers.

Between-group comparisons of 2D-BioPAD AD plasma biomarker levels will be conducted using e.g., Mann-Whitney U test, t-test, or ANOVA as appropriate. Groups will be defined according to both clinical and biomarker-based characteristics. Diagnostic groups will be based on diagnosis established following centre-specific standard assessments, e.g., AD dementia, other dementia, MCI, or control. Biomarker-based groups will be defined using:

- For all participants, AD blood biomarkers measured with benchmarking equipment. Cut-offs will be based on existing literature (where available) and/or data-driven, e.g., using Gaussian mixture modelling.
- For participants with available AD CSF biomarkers from standard assessments, grouping will be based on established cut-offs.
- Exploratory analyses will consider ATN-based categorizations using state-of-the-art CSF and/or benchmarking plasma biomarkers.

To assess the potential impact of other parameters, e.g., demographics, comorbidities, liver and/or kidney function, APOE genotype (where available), such parameters will be added as covariates in the analyses.

Discrimination accuracies of 2D-BioPAD AD plasma biomarkers will be determined with logistic regression models and receiver operating characteristic curve (ROC) analysis. When predicting diagnosis or CSF-based biomarker +/- status, for each AD blood biomarker the area under the receiver operating characteristic curve (AUC) of the ROCs for 2D-BioPAD and benchmarking measures will be compared with DeLong test. Sensitivity, specificity, positive and negative predictive values will be assessed for different 2D-BioPAD biomarker cut-offs. Initial analyses will consider each AD plasma biomarker individually. Further analysis will investigate combinations of plasma biomarkers to determine which combinations have the best discrimination accuracy.

AD plasma biomarkers (2D-BioPAD versus benchmarking equipment) will be investigated in relation to cognitive, clinical, and other data using appropriate regression models.

Unadjusted 2-sided p-values <0.05 will be considered statistically significant. Adjustment for multiple testing using a false discovery rate (e.g., Benjamini-Hochberg procedure) will be used where relevant.

The main hypothesis is that the accuracy of the 2D-BioPAD system measurements is noninferior to the accuracy of AD plasma biomarkers measured using benchmarking equipment.

Analyses of user experience (HCPs and patients) will include mainly descriptives, with comparisons by country, clinical specialty, and/or years of experience where relevant.

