Clinical pilot study coordination (UEF, GAADR, ZI)	Activities as describe above. As the Task 5.1 leader, UEF was responsible for the coordination of the work.
Ethics & regulatory (EVNIA)	Read the clinical pilot study initiation package and provided key input on ethical aspects and overall content input for all documents. Developed the 2D-BioPAD Questionnaire Surveys for patients and HCPs. Led the work on regulatory aspects of the clinical pilot study (see also section 4.1.5 Ethical and regulatory aspects).
Technical (ICN2, NOVA, AUTH, UP-CATRIN, GRAPHEAL, CeADAR)	Read documents related to the clinical pilot study circulated by the Task leader and provided input where applicable. Provided continuous information about work on technical aspects with relevance for the clinical pilot study design.
Management (QPLAN)	Reviewed all documents circulated by the Task leader. Interaction in terms of timeline and expectations as per the GA. Alignments with T1.1 findings.

4.1.3. *Harmonisation of assessment procedures across clinical study centres*

To ensure harmonisation of clinical pilot study procedures across the three study centres, a detailed mapping of centre-specific standard procedures was first conducted, covering the following aspects:

A) *Standard diagnostic procedures*

General

- Diagnostic criteria
- Estimated changes in diagnostic criteria in the near future
- Use of consensus diagnosis and details on the diagnostic process

All clinical study centres use International Classification of Diseases (ICD)-10 based diagnostic coding in medical records. This is not expected to change for the duration of the 2D-BioPAD clinical pilot study. Diagnostic criteria are overall well aligned. While there are differences in referral pathways based on healthcare system organisation and specialty (e.g. Neurology in Finland and Greece, Psychiatry in Germany), there are significant similarities in the overall diagnostic process and the use of multidisciplinary teams. Consensus diagnosis is consistently used for cases that are less clear-cut or require additional discussion of diagnostics and treatment.

Follow-up schedule

- Which patient groups are followed-up over time
- Follow-up intervals
- Assessments included in follow-up visits

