4.2.1. Blood samples and selection criteria

Existing samples will be used if they are maximum 10 years old, continuously stored in -70°C freezer since collection, and there is consent for use of the samples and related clinical data, including shipping/sharing within the EU.

Table 4. Inclusion and exclusion criteria for the retrospective study

Inclusion criteria	
Plasma samples	
 • Maximum 10 years old • Up to 2 ml available for 2D-BioPAD pilot study • Stored in -70°C freezer • Existing consent to re-use for research, including shipping within the EU
Sample-related clinical data	
 • Diagnosis AD dementia, MCI due to AD, or no dementia-related disease (control) in connection to the blood sample collection time • Available data on CSF biomarkers, cognitive tests (at least MMSE), comorbidities, and medications in connection to the diagnostic workup • Existing consent to re-use data for research, including sharing within the EU
Exclusion criteria	
Sample-related clinical data	
 • Diagnosis of dementia other than AD • Mixed dementia • MCI suspected due to non-AD causes, as per clinical judgement based on centre-specific standard assessments

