4.3.4.1. At the 2D-BioPAD baseline visit

Data (including existing data from centre-specific standard assessments) will be collected for use in this study only after the informed consent form has been signed.

Table 6. Data collected from patients

Existing data from centre-specific standard assessments
Cognitive status 
 • Control / no dementia disease / subjective cognitive complaints • MCI • Dementia type • Date of diagnosis
Demographics, e.g.: 
 • Age • Gender (as recorded in medical records) • Years of formal education • Civil status • Work status
Family history of AD/other dementias in first degree relatives
#Neuropsychological test results and function in activities of daily living according to the standard diagnostic protocol of the respective centre.
Medical history (ICD-10 codes)
Current medication (ATC codes)
Markers of kidney and liver function, e.g., creatinine (with the Chronic Kidney Disease Epidemiology Collaboration CKD-EPI equation used to estimate glomerular filtrate rate, eGFR) and ASAT; other centre-specific markers may include e.g., urea, ALAT, GGT, CPK)
Systolic and diastolic blood pressure
Height and weight, BMI
Semiquantitative/visual brain MRI ratings if available (e.g., MTA, Fazekas)
*Results of CSF biomarker analysis according to the centre-specific standard protocol (e.g., A β 40, A β 42, total tau, ptau-181) if available
Results of genetic testing (APOE genotype) if available
Amyloid-PET visual ratings (e.g., positive/negative) if available
Visual readings of FDG-PET scans if available
New data
Blood sample for measurement of plasma AD biomarkers (A β 40, A β 42 and the A β 42/40 ratio, p-tau217, NfL, GFAP) using benchmarking equipment **
Blood sample for measurement of plasma AD biomarkers using the 2D-BioPAD diagnostic aid
Questionnaire including feedback about experience with 2D-BioPAD diagnostic aid
Self-reported lifestyle questionnaire

A minimum set of tests conducted at all study centres should include:

- Mini Mental State Examination (MMSE)
- Consortium to Establish a Registry for Alzheimer's Disease (CERAD)
- Alzheimer's Disease Cooperative Study Activities of Daily Living inventory (ADCS-ADL)
- Montgomery-Asberg Depression Rating Scale (MADRS)

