4.3.4.3. At follow-up

For all 300 patients, up to 1 year follow-up after baseline will be included if the diagnosis is unclear at baseline and follow-up is scheduled as per centre-specific standard procedures. The following patient-related data will be collected:

- Cognitive status
 - Control / no dementia disease / subjective cognitive complaints
 - MCI
 - Dementia type
- Date of diagnosis

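### The prospective study records MCI without its cause, so its primary accuracy measures for AD diagnosis are undefined for MCI and biased if all MCI is put on one side

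*Protocol*

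**What the plan says.** Table 9 (Protocol 4.4.2) sets the prospective primary accuracy outcome as sensitivity, specificity and predictive values of the device versus the benchmark "for identifying AD diagnosis established as per centre-specific standard procedures". It does not say whether that means AD dementia alone or also MCI due to AD.

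The cognitive-status item in Table 6 (4.3.4.1) reads "Control / no dementia disease / subjective cognitive complaints • MCI • Dementia type". Section 4.3.4.3 repeats these categories at follow-up, where "up to 1 year follow-up after baseline will be included if the diagnosis is unclear at baseline". At both visits the only entry that carries a cause is "Dementia type".

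Section 4.4.3 names diagnostic groups for comparing biomarker levels: "Diagnostic groups will be based on diagnosis established following centre-specific standard assessments, e.g., AD dementia, other dementia, MCI, or control". Its accuracy paragraph speaks only of predicting diagnosis and gives no rule for MCI.

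Other parts of the protocol bear on this:
- Table 5 admits any MCI to the prospective study, whatever the cause.
- Table 4 (retrospective study) admits MCI due to AD and excludes MCI suspected of a non-AD cause, by clinical judgement from each centre's standard work-up.
- Table 3 includes the prodromal stage in the device's intended population.

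**The concern.** A patient with MCI due to AD and a patient with MCI of another cause get the same entry. To fill the primary two-by-two table, the analyst must call every MCI patient non-AD, call every one AD, or leave them all out. The first makes a correct positive result in prodromal AD a false positive. The second makes a correct negative result in non-AD MCI a false negative. The third removes the early-stage group that the introduction and Table 3 give as a reason for the device.

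Follow-up does not solve this. A patient who progresses gets a dementia type, but one whose MCI is attributed to AD during the year is still entered as MCI.

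An analysis plan can define the target condition. It cannot supply a cause that was never recorded.

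**Working it through.** The protocol states no expected accuracy, case mix or MCI aetiology, so there is no figure of its own to reproduce. Everything below is illustrative.

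**Assumed inputs.** 300 patients: 100 AD dementia, 60 MCI due to AD, 60 other MCI, 80 other (controls and other dementia). Sensitivity is 0.90 in AD dementia and 0.85 in MCI due to AD; specificity is 0.90. Only the total of 300 comes from the protocol.

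**Marker-positive patients.** AD dementia 100 × 0.90 = 90; MCI due to AD 60 × 0.85 = 51; other MCI 60 × 0.10 = 6; other 80 × 0.10 = 8. That is 155 positive and 145 negative.

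**Results by rule.** The first row takes AD dementia or MCI due to AD as the target.

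| Rule for MCI | Sensitivity | Specificity | PPV | NPV |
|---|---|---|---|---|
| Split by cause | 141/160 = 88.1% | 126/140 = 90.0% | 141/155 = 91.0% | 126/145 = 86.9% |
| All MCI non-AD | 90/100 = 90.0% | 135/200 = 67.5% | 90/155 = 58.1% | 135/145 = 93.1% |
| All MCI AD | 147/220 = 66.8% | 72/80 = 90.0% | 147/155 = 94.8% | 72/145 = 49.7% |
| MCI left out | 90/100 = 90.0% | 72/80 = 90.0% | 90/98 = 91.8% | 72/82 = 87.8% |

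The last row uses 180 patients; 120/300 = 40% are lost.

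**A second mix.** Take 100 AD dementia, 100 MCI of whom 40 are due to AD, and 100 other. With all MCI as non-AD, specificity is (160 × 0.90 + 40 × 0.15)/200 = 150/200 = 75%, and PPV is 90/(90 + 34 + 16) = 64% against (90 + 34)/140 = 89%. Leaving MCI out loses 100/300 = 33%.

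**Range under other assumptions.** Three case mixes were tried (AD dementia/MCI/other dementia/control 100/100/40/60, 75/75/50/100 and 90/120/30/60), with 30-70% of MCI due to AD, specificity 0.85, and sensitivity 0.85 in dementia and 0.85 or 0.75 in MCI due to AD. With all MCI as non-AD, specificity is 0.57-0.79 against 0.85, PPV 0.46-0.64 against 0.73-0.89, and NPV 0.89-0.94 against 0.76-0.92. Sensitivity shifts only when the marker performs differently in MCI due to AD: it is then 0.85 against 0.80-0.83.

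**Device versus benchmark.** In the first mix, let the device detect 70% of MCI due to AD and the benchmark 85%, all else equal. The device then finds 60 × 0.70 = 42 of these patients.
- Split by cause: sensitivity (90 + 42)/160 = 82.5% against 88.1%. The device is worse.
- All MCI non-AD: sensitivity 90% for both; device specificity (126 + 18)/200 = 72% against 67.5%. The device looks better.
- All MCI AD: sensitivity (90 + 42 + 6)/220 = 62.7% against 66.8%. The device is worse, by less.
- MCI left out: no difference.

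If the two methods perform alike in every patient group, no rule creates a difference between them.

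**The case against.** The strongest reply is that Table 6 is a list of data items, not a CRF. The CRFs are still to be designed (4.3.5.4) and an updated protocol is in preparation (section 5). Section 4.2.2 also writes plain MCI for the retrospective study, where the cause is known, so the bare word need not mean that cause goes unrecorded. The first two statements are true and make the repair cheap. The third does not carry over: Table 4 has already restricted the retrospective sample by cause, and Table 5 does not.

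Three stronger readings are tempting, and the documents do not support them.
- *That MCI due to AD cannot be counted as AD at all.* "All clinical study centres use International Classification of Diseases (ICD)-10 based diagnostic coding in medical records" (section 4.1.3), and Table 6 collects ICD-10 codes, CSF, amyloid-PET and FDG-PET where available. Some patients could be recovered. But CSF is expected in a third to a half of patients and is taken on clinical indication and consent, PET is done in selected cases, and none of these is tied to the primary reference diagnosis. CSF-defined pathology is a separate secondary outcome.
- *That the primary measures are wrong.* The protocol chooses no rule, so they are undefined. The section 4.4.3 group list is illustrative and concerns biomarker levels, not the accuracy table. No single rule distorts every measure, and leaving MCI out mislabels nobody.
- *That noninferiority becomes easier to claim.* This depends on the rule and on where the two methods differ. With all MCI as non-AD, a deficit in prodromal AD is hidden, but a deficit confined to AD dementia shows undiluted in sensitivity.

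It is also fair that this is a pilot meant to give preliminary information, and that the secondary pathology outcome assesses early disease without using the MCI label. That lowers the severity but does not define the primary outcome.

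**Conclusion.** The point holds as a gap in the listed data and in the definition of the primary target. Collected exactly as listed, the diagnosis fields cannot place MCI due to AD in the primary two-by-two table, and a later analysis plan could repair this only partly.

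The size rests wholly on assumed case mix and accuracy. In the main example, calling all MCI non-AD lowers specificity by 22.5 points (90.0 − 67.5) and PPV by about 33 (91.0 − 58.1), and raises NPV by about 6 (93.1 − 86.9). Calling all MCI AD lowers sensitivity by about 21 points (88.1 − 66.8) and NPV by about 37 (86.9 − 49.7). These shifts are biases if the target is AD dementia or MCI due to AD. If AD dementia alone is meant, the 67.5% is the right specificity for that target, but detecting prodromal AD then counts against the device. The protocol needs to say which it means.

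This should be fixed before the CRFs are built.

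**What to change.** 1. In Table 6 and section 4.3.4.3, replace the single MCI entry with three: due to AD, not due to AD, and cause undetermined. Use the same centre-specific clinical judgement that Table 4 relies on. The undetermined category is new; Table 4 has none.
2. In Table 9, define AD diagnosis as AD dementia or MCI due to AD, against all other determined diagnoses. Report undetermined MCI as a separate stratum.
3. Give the accuracy for AD dementia only as a secondary analysis.

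The cost is one CRF field at each of two visits and one sentence in Table 9, while the CRFs (due by M24) and the updated protocol are still open. The downside is that some MCI patients will be undetermined and will leave the primary two-by-two table, so their number should be reported beside it.
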